### 3.4. Statistical framework

The ACTION trial will use a superiority testing framework, with the active treatment arm (azithromycin) compared against placebo.

The analysis will account for interim analyses using a group-sequential testing framework using the Lan-DeMets spending function approach with an O'Brien and Fleming boundary [2].

### 3.5. Statistical interim analyses and stopping guidance

Due to uncertainty in the possible effects of treatment and the urgency of identifying effective therapies for COVID-19, sequential randomized controlled trials with interim monitoring are expected to provide robust results faster than standard fixed parallel trials without interim monitoring [3]. In the absence of a significant difference between randomized arms, the study team believes that there is value in continuing the randomized comparison of Azithromycin versus placebo to full enrollment (i.e., 455 participants) in order to obtain as much precision as possible and to provide maximal information to inform the field. We therefore have not recommended interim analyses for futility.

#### Interim analyses for efficacy

We have assumed 1 interim analysis at 50% of participants with 14-day endpoints measured using a Lan-DeMets spending approach with an O'Brien-Fleming boundary. The actual alpha spending will be updated according to the actual interim analysis schedule, should trial investigators change the schedule in coordination with the trial's DSMC.

A summary of the interim analysis and nominal  $P$ -values is below, created by the R package `gsDesign`. We have also included a summary of standardized treatment effects along the efficacy bound, For additional details see this SAP's companion computational notebook: `ACTION-sample-size-power-symptom-free.Rmd / .html`.

```
## One-sided group sequential design with
## 80 % power and 2.5 % Type I Error.
##
## Analysis N Z Nominal p Spend
## 1 228 2.96 0.0015 0.0015
## 2 456 1.97 0.0245 0.0235
## Total 0.0250
##
## ++ alpha spending:
## Lan-DeMets O'Brien-Fleming approximation spending function with none = 1.
##
## Boundary crossing probabilities and expected sample size
## assume any cross stops the trial
##
## Upper boundary (power or Type I Error)
## Analysis
## Theta 1 2 Total E{N}
## 0.0000 0.0015 0.0235 0.025 454.8
## 0.1316 0.1641 0.6359 0.800 417.9
```

We note the pre-specification of a flexible alpha spending function permits interim analysis at the discretion of the DSMC. We will update the efficacy bound according to the trial's actual interim analysis schedule.

The DSMC will review interim analyses and will make a recommendation to stop the trial for efficacy after each review. Early stopping for any reason will mandate final analysis at alpha of the full final prespecified value based on all available data (incorporating any alpha spending, as needed). In considering possible modifications to the study or termination of the study, the DSMC may consider other outcome measures than the composite hospitalization/death outcome measure. For example, the DSMC might make recommendations based on a high level of evidence for a difference between randomized arms in the proportion dying. A "high level of evidence" might be based on application of the O'Brien and Fleming stopping guideline to the death outcome.

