15.4 Procedures to Ensure Confidentiality and Proper Communication

To enhance the integrity and credibility of the trial, procedures will be implemented to ensure the DSMC has access to all emerging information from the trial regarding comparative results of efficacy and safety, aggregated by treatment arm.

Closed Sessions

Sessions involving only DSMC members and, where appropriate, those unmasked trial investigators (on the Data Coordinating Committee) who generate the Closed Reports (called Closed Sessions) will be held to allow discussion of confidential data from the trial, including information about the relative efficacy and safety of interventions.

At a final Closed Session, the DSMC will develop a consensus on its list of recommendations, including that relating to whether the trial should continue.

Open Session

In order for the DSMC to have access to information provided, by study investigators, or members of regulatory authorities, a joint session between these individuals and DSMC members will be held between the Closed Sessions.

Open and Closed Reports

For each DSMC meeting, Open and Closed Reports will be provided. Open Reports, will include data on recruitment and baseline characteristics, pooled data on eligibility violations, and completeness of follow-up and compliance. The study statistician ([name]) will prepare these Open Reports.

Closed reports, available only to those attending the Closed Sessions of the meeting, will include analyses of primary and secondary efficacy endpoints, including subgroup and adjusted analyses, AEs and symptom severity, and Open Report analyses that are displayed by intervention group. These Closed Reports will be prepared by the study biostatistician.

The Open and Closed Reports should provide information that is accurate, with follow-up that is complete to within two months of the date of the DSMC meeting. The Reports should be provided to DSMC members approximately three days prior to the date of the meeting.

Minutes of the DSMC Meeting

The research team will prepare minutes for the open portion of the meeting, including the DSMC's recommendations.

Recommendations to the Steering Committee (SC)

At each meeting of the DSMC during the trial, the committee will make a recommendation to the Steering Committee to continue or terminate. This recommendation will be based primarily on safety and efficacy considerations and will be guided by statistical monitoring guidelines defined in this Charter.

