### 3.3. Sample size

The trial's revised target enrollment is 455 participants, which will be sufficient to detect an increase in the proportion of patients who are symptom free 50% to 65% (15 percentage point increase) at 14 days from enrollment.

With 455 participants, the trial will have 80% power to detect an increase of 15 percentage points in the percentage of patients who are symptom free at 14-d under the following assumptions:

- 2:1 allocation ratio of azithromycin : placebo
- 50% symptom-free under placebo at the 14-day measurement (binomial outcome)
- 20% loss to follow-up
- 2-sided alpha of 0.05, power = 0.8.

- A single interim analysis with 50% of primary outcomes collected with stopping guideline determined using the Lan-DeMets spending function approach with an O'Brien and Fleming boundary.

The table below shows sample sizes under several effect size scenarios, assuming azithromycin increases the proportion of patients who are symptom free by 0.1 to 0.2 compared to placebo.

Sample size required for a fixed design allowing for 20% loss to follow-up. Calculations assume 2-sided alpha of 0.05 and 80% power.

p placebo	p azithro	RD	N placebo	N azithro	N Total
0.5	0.60	0.10	348	695	1,043
0.5	0.61	0.11	287	573	860
0.5	0.62	0.12	240	479	719
0.5	0.63	0.13	204	407	611
0.5	0.64	0.14	175	349	524
0.5	0.65	0.15	152	303	455
0.5	0.66	0.16	133	265	398
0.5	0.67	0.17	117	233	350
0.5	0.68	0.18	104	207	311
0.5	0.69	0.19	93	185	278
0.5	0.70	0.20	83	165	248

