### 3.6. Timing of the final analysis

The final analysis will take place when 14-day outcomes have been measured on all participants. If the trial is stopped for efficacy or for any other reason before the full sample, the final analysis will include all outcomes among patients who have been enrolled at the time the trial is stopped.

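### SAP 3.5 tests at the full final alpha after early stopping for any reason, so 5% type I error is not guaranteed when the stop was informed by results by arm

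*SAP*

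**What the plan says.** SAP 3.3 sets "2-sided alpha of 0.05, power = 0.8". The gsDesign output in SAP 3.5 is one-sided, with "80 % power and 2.5 % Type I Error". Its interim row reads "1 228 2.96 0.0015 0.0015": analysis 1, N=228, Z=2.96, nominal p and spend 0.0015. The final row has N=456, Z=1.97 and nominal p 0.0245, which is 0.049 two-sided and agrees with the final level in Protocol 3.5.

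On early stopping, SAP 3.5 says: "Early stopping for any reason will mandate final analysis at alpha of the full final prespecified value based on all available data". The sentence ends with a parenthesis, "incorporating any alpha spending, as needed". It adds that, when modification or termination is considered, "the DSMC may consider other outcome measures than the composite hospitalization/death outcome measure". It also lets the DSMC add looks, with the bound updated. SAP 3.6 says which data are used: "If the trial is stopped for efficacy or for any other reason before the full sample, the final analysis will include all outcomes" among those enrolled at the stop.

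Under Protocol 15.4 the DSMC receives efficacy by arm in Closed Reports, and at each meeting "the committee will make a recommendation to the Steering Committee to continue or terminate". The Steering Committee takes the decision. SAP 4.1 and 6.2 say only that significance follows the alpha-spending function.

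**The concern.** The spending function releases little alpha at half the information because the result will be looked at again. All the remaining alpha may be used at an earlier point only if the reason for ending there has nothing to do with the observed treatment difference; slow enrollment judged on masked data is an example. If the people who recommend the stop have seen the difference, the stop can select favourable interim results, and a test at 1.97 then takes no account of that selection.

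SAP 3.5 treats both kinds of stop alike. An interim Z of 2.3, for example, fails the 2.96 boundary. If the trial were then ended on some other stated ground, the rule as written would judge those data, plus whatever came in afterwards, against about 1.97. Neither document says that a stop short of the boundary cannot be declared positive. At stake is whether a positive claim after such a stop would carry the stated 5% error rate.

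**Working it through.** **Inputs.** Overall alpha 0.025 one-sided (0.05 two-sided), one look at information fraction 0.5, and Lan-DeMets O'Brien-Fleming spending (SAP 3.3 and 3.5). Data after a stop: everyone enrolled by then (SAP 3.6). The share of cases stopped, the amount of overrun and the correlation with other outcomes are not in the documents; they are assumptions, shown as ranges.

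**1. The plan's boundaries reproduce.** Spending is α(t) = 2 − 2Φ(2.2414/√t), where 2.2414 is the 0.9875 normal quantile. At t = 0.5, 2.2414/0.7071 = 3.170 and α = 0.00153, so the interim Z is 2.963. With correlation √0.5 between looks, solving P(Z1 < 2.963, Z2 < c) = 0.975 gives c = 1.969, nominal 0.0245 one-sided. These match the SAP's 2.96, 1.97, 0.0015 and 0.0245.

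**2. Stop unrelated to results.** Testing at 1.969 gives 2.45% to 2.5% one-sided, whatever the chance of such a stop. The rule is harmless here.

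**3. Always stopping when the interim Z is between 1.97 and 2.96, no overrun.** Under the null, P(1.969 < Z1 < 2.963) = 0.0230. Of this, 0.0072 would also have exceeded 1.969 at full enrollment and is already counted. The addition is 0.0230 − 0.0072 = 0.0158, so one-sided error is 0.0250 + 0.0158 = 0.0408. Counting both directions, P(|Z1| > 1.969 or |Z2| > 1.969) = 0.0815.

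**4. Stopping in only some of these cases.** Two-sided error is 5.0% plus the share times 3.15 points (8.15 − 5.0).

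| Share stopped | Two-sided error |
|---|---|
| 25% | 5.8% |
| 50% | 6.6% |
| 75% | 7.4% |
| 100% | 8.2% |

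**5. Adding overrun.** Suppose the stopped trial is analysed at information f above 0.5. The error is P(|Z1| > 2.963), plus P(1.969 < |Z1| < 2.963 and |Zf| > 1.969), plus P(|Z1| < 1.969 and |Z2| > 1.969). Zf and Z1 have correlation √(0.5/f).

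| f at analysis | Two-sided error |
|---|---|
| 0.51 | 7.5% |
| 0.55 | 6.8% |
| 0.60 | 6.3% |
| 0.70 | 5.7% |

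A stopping threshold tuned to the overrun, somewhat below 1.97, raises these by about 0.2 to 0.3 points.

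**6. Does the parenthesis cure it?** Solving again so that cumulative one-sided alpha equals 0.025 at the stop gives a critical value of about 1.96. The no-overrun error is then 8.2% to 8.3%. The parenthesis would help only if it capped alpha at the amount spent so far, which contradicts the main clause.

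**7. Stop driven only by another outcome.** Suppose the trial stops when another null outcome passes 1.96 or 2.96, and that outcome has correlation 0 to 0.6 with the primary. Two-sided error is 5.0% to 5.5%.

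**The case against.** The strongest reply is that the worst case needs a policy that nobody has proposed. SAP 3.5 says that, without a significant difference, there is value in continuing to 455 participants, and it sets no futility look. Protocol 15.4 has recommendations guided by the monitoring guidelines. SAP 4.1 and 6.2 tie significance to the spending function, and the bound is updated to the actual schedule. Overrun reduces the error, and the two-sided figure counts stops in which azithromycin looked worse. Much of this stands: it limits how likely and how large the inflation is. It does not remove the rule. None of these passages says which threshold applies after a stop short of the boundary; the sentence in 3.5 does, and it gives the full final value.

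A reader might make three stronger inferences that the documents do not support:

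- **That the DSMC itself can stop the trial and make it positive.** The DSMC advises; the Steering Committee decides.
- **That its freedom to consider other outcomes produces the 8%.** That route alone gives 5.0% to 5.5% at the assumed correlations. The SAP's own example is deaths, at a high level of evidence. The 8% needs a stop that tracks the primary result.
- **That the error must exceed 8% because looks can be added.** Repeated stopping at 1.97 over looks at 25, 50, 75 and 100% would give about 12%, but the plan has one look and updates the bound if more are added.

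**Conclusion.** The point holds as a loss of guaranteed control. It is not a forecast of 8% error. As written, SAP 3.5 lets a below-boundary result be declared significant after a stop informed by results by arm, and no other passage prevents this.

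The ceiling for one look at 50% information is 4.1% one-sided against 2.5%, or 8.2% two-sided against 5%. It requires a stop every time the interim Z falls between 1.97 and 2.96, and no overrun. Overrun to information 0.51 to 0.70 brings the two-sided figure to about 7.5% to 5.7%. The range is assumed because no accrual rate is given. Occasional stopping lowers the error further. If the trial runs to its planned end, or stops for reasons unrelated to results by arm, the error stays at or just below 5%.

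**What to change.** Replace the sentence in SAP 3.5 with two rules:

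- **(a)** The full remaining alpha is used only when the stop is documented as unrelated to unmasked results by arm (for example enrollment, drug expiry or funding), whoever recommends it.
- **(b)** After any other stop where the boundary was not crossed, the primary outcome is called significant only if it meets the Lan-DeMets O'Brien-Fleming boundary for the information fraction in the data analysed, including overrun under SAP 3.6 and taking account of alpha already spent. Otherwise estimates and intervals are reported without a claim of significance.

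As a check on (b), α(0.55) = 0.0025 and α(0.70) = 0.0074. After the 0.0015 spent at the interim, the boundaries are Z = 2.87 and Z = 2.46. With a stop every time the interim Z is in the 1.97 to 2.96 zone, two-sided error is then 3.8% and 4.4%, within 5%.

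The cost is two sentences and a stricter efficacy threshold after a results-informed early stop. Sample size, look schedule and the DSMC's freedom to recommend stopping are unchanged.

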### 3.6. Timing of the final analysis

The final analysis will take place when 14-day outcomes have been measured on all participants. If the trial is stopped for efficacy or for any other reason before the full sample, the final analysis will include all outcomes among patients who have been enrolled at the time the trial is stopped.

### 3.7. Timing of outcome assessments

Primary outcomes will be measured 14-days after enrollment. Additional visits will take place at 3, 7, and 21 days after enrollment. Protocol section 3.2 includes details about the trial profile.

## **4. Statistical Principles**

### **4.1. Confidence intervals and *P*-values**

The trial will report 95% confidence intervals and permutation *P*-values estimated from the primary analysis. The level of statistical significance will depend on the alpha spending function that accounts for the group sequential design (see section 3.5 for details).

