8.6 Laboratory Technicians

- Prepare patient study kits with all materials needed for the study
- Organize study supplies
- Prepare patient information sheets and swab instructions
- Scan swabs received from the participants into the REDCap database
- Assist with laboratory analysis of samples
- Assist with biobanking and storage of specimens

9 Statistical Methods

Please see the Statistical Analysis Plan for details on pre-specified statistical methods for this trial.

The primary analysis will estimate the risk difference (RD) and risk ratio (RR) comparing azithromycin to placebo. We will estimate these parameters using a logistic regression model with a single covariate for treatment arm. We will estimate the RD and RR from the logistic regression using marginal standardization, and a bootstrap for 95% confidence intervals [5,6]. We will compute *P*-values for differences between arms using a permutation test with the difference between arms as the test statistic and 10,000 iterations.

The secondary analysis of viral load will compare log transformed values of relative read and number of reads using a t-test. We will compute *P*-values for differences between arms using a permutation test with the difference between arms as the test statistic and 10,000 iterations.

Determination of statistical significance for the primary and secondary analysis will follow the final alpha-spending function determined by the group sequential design.

10 Study Medication

The study drug product will be obtained from Pfizer, Inc. Participants enrolled in the study will be offered a dose of oral azithromycin or placebo determined by their randomization allocation. We will monitor adverse events following treatment as described in Chapter 9.

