### 6.2. Analysis methods

#### Primary Outcome:

The primary analysis will estimate the risk difference (RD) comparing the proportion of patients who are symptom-free at 14 days in the azithromycin versus placebo arms. We will compute *P*-

values for differences between arms using a permutation test with the prevalence difference between arms as the test statistic and 10,000 iterations. We will additionally estimate and report the prevalence ratio.

Determination of statistical significance for the primary and secondary analyses will follow the final alpha-spending function determined by the interim analyses (see section 3.5).

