## 6.2. Analysis methods

### Primary Outcome:

The primary analysis will estimate the risk difference (RD) comparing cumulative incidence of hospitalization or death by 14 days in the azithromycin versus placebo arms. Kaplan-Meier approach to account for losses to follow-up. We will use Greenwood's formula to estimate the standard error of the log proportion in each arm will be used to determine the variance of the risk difference, and will report 95% confidence intervals adjusted for interim analyses. We will compute *P*-values for differences between arms using a permutation test with the risk difference between arms as the test statistic and 10,000 iterations. We will additionally estimate and report the risk ratio.

Determination of statistical significance for the primary and secondary analyses will follow the final alpha-spending function determined by the group sequential design (see section 3.5).

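### If the trial stops early for efficacy, the plan provides no sequentially adjusted interval or estimate, so the reported benefit would be too large on average and, for true effects up to about 20 points, its 95% interval would cover too rarely

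*SAP*

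**What the plan says.** **Design.** SAP 3.5 keeps one efficacy look: "We have assumed 1 interim analysis at 50% of participants with 14-day endpoints measured using a Lan-DeMets spending approach", with an O'Brien-Fleming boundary. The printed boundary is Z = 2.96 at the interim and 1.97 at the end. On stopping, "The DSMC will review interim analyses and will make a recommendation to stop the trial for efficacy after each review". SAP 3.6 says the final analysis of a stopped trial includes the outcomes of everyone enrolled at that time.

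**Testing.** SAP 4.1: "The level of statistical significance will depend on the alpha spending function that accounts for the group sequential design". SAP 6.2 repeats this for the primary and secondary analyses.

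**Estimation.** SAP 6.2: "The primary analysis will estimate the risk difference (RD) comparing the proportion of patients who are symptom-free at 14 days". It adds a permutation P-value and a prevalence ratio but no interval method. SAP 4.1 says "The trial will report 95% confidence intervals and permutation" P-values, without saying how the intervals are built. Protocol section 9 gives the only method: the risk difference from a logistic model by marginal standardization "and a bootstrap for 95% confidence intervals".

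**Superseded version 5, appended to the SAP.** It said the trial "will report 95% confidence intervals adjusted for interim analyses". The current SAP has no such provision, and the version 6 entry in the revision history does not mention its removal.

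**Threshold.** Protocol 3.5 tests efficacy at the interim at p = 0.001. The SAP boundary is 0.0015 one-sided, about 0.003 two-sided.

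**The concern.** A trial that stops early does so because its observed difference was large. The raw difference from such a trial is therefore biased upwards, and an interval built as if no look had taken place is centred too high. Spending alpha protects the test but does nothing for the estimate or the interval.

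An early efficacy stop is also the result most likely to be acted on. The effect size and interval would be the headline figures, and a method chosen after the stop is open to dispute.

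**Working it through.** **1. Reproduce the SAP boundary.** Inputs from SAP 3.3 and 3.5: one-sided alpha 0.025, information fraction 0.5, Lan-DeMets O'Brien-Fleming spending.

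- Alpha spent at the interim = 2[1 − Φ(z₀.₉₈₇₅/√0.5)] = 0.001525, so Z = 2.963.
- The final Z solves P(Z₁ ≥ 2.963 or Z₂ ≥ c) = 0.025 with correlation √0.5. This gives c = 1.969, nominal p = 0.0245.
- The drift for 80% power is 2.807, so P(stop at the interim) = 1 − Φ(2.963 − 2.807 × 0.7071) = 0.164.

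All agree with the printed 2.96, 1.97, 0.0245 and 0.1641.

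**2. Difference needed to stop.** 455 less 20% loss leaves 364 evaluable, split 2:1 as 121 placebo and 243 azithromycin, with 61 and 121 at the interim. At 50% v 65%:

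- SE = √(0.25/60.7 + 0.2275/121.3) = 0.0774, so the boundary is 2.963 × 0.0774 = 22.9 points.
- If all 228 at the interim are evaluable (76 and 152): SE = √(0.25/76 + 0.2275/152) = 0.0692, so the boundary is 20.5 points.

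Any trial that crosses therefore shows a difference at the look well above the planned 15 points.

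**3. Simulate the reported result.** Two-stage binomial trials, placebo rate 50%, SAP boundary, raw risk difference ± 1.96 SE. Overrun means participants enrolled but not yet assessed at the look, whose outcomes SAP 3.6 adds. The documents give no figure for it. The range of 10–20% of the final sample is an assumption.

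| True difference | Chance of stopping | Overrun | Mean reported if stopped | 95% interval coverage if stopped |
|---|---|---|---|---|
| 10 points | about 5% | none | 26.2 | 38–39% |
| 10 points | about 5% | 10–20% | 23.5–21.6 | 51–61% |
| 15 points | about 16% | none | 26.8 | 82% |
| 15 points | about 16% | 10–20% | 24.9–23.5 | 81–83% |
| 20 points* | 35% | none | 28.2 | 93.0% |
| 25 points* | 60% | none | 29.9 | 95.9% |

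*Normal approximation.

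Sensitivity at a true 15 points, no overrun:

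- With 228 and 456 evaluable: stop 21.7%, mean 24.3 points, coverage if stopped 86.3%.
- With the Protocol's interim p = 0.001: stop about 9%, mean about 29 points, coverage if stopped about 69%.

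Over all trials, stopped or not, coverage is 94.1% at 15 points (94.8% with no interim look) and 93.1% at 10 points. Average bias is +0.9 points at the planned effect and at most about +1.5.

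**4. What a repeated interval does.** It is the estimate ± the critical value of the stopping look × SE.

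- Trial exactly on the interim boundary: the ordinary interval is 22.9 ± 1.96 × 7.74, or 7.8 to 38.1 points. The repeated interval is 22.9 ± 2.963 × 7.74, or 0.0 to 45.9. Whitehead's bias-adjusted estimate is 21.4.
- Trial that runs to the end with Z = 2.8: the estimate is 15.3, and both intervals are 4.6 to 26.1 to one decimal.
- Without overrun, the repeated interval covers 98.6% of stopped trials at a true 15 points and 95.4% at 10 points. Overall it covers 96.8% and 95.8%.
- An interval from stage-wise ordering equals the ordinary one at the first look, so it would not help there.

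**The case against.** **The SAP is silent; it does not choose an ordinary interval.** SAP 3.4 says the analysis will account for interim analyses, and SAP 3.5 speaks of incorporating alpha spending as needed. A reader might infer a decision to ignore the look, or read the version 5 wording as a contradiction. The documents support neither: SAP 6.2 names no interval method, and version 5 is superseded. What stands is that the only method named anywhere, in Protocol section 9, is unadjusted, and that the sequential provisions attach to testing. An analyst who follows the text would report the raw figures.

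**Interim-only figures are not the reported analysis.** This is right. SAP 3.6 adds the overrun, which lowers the mean and raises coverage at a true 10 points. It does not remove the problem: coverage at 15 points stays at 81–83%.

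**The harm is conditional.** This is also right. A reader might infer that the interval fails in general, or that type I error is inflated. Neither follows. Coverage over all trials is close to nominal, coverage after a stop is nominal near a true 25 points, and a stop under no effect has a chance of about 0.15%. The gap between 1.96 and 1.97 at the final look is about 0.5% of the interval's width.

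**The remedy is imperfect.** The repeated interval is conservative at the planned effect. Without overrun it covers only 79% of stopped trials at a true 5 points and none at a true zero. Such stops are rare (about 1% and 0.15%), but the limitation stands.

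**Conclusion.** The concern holds for a trial that stops early. At the planned effect that is about one trial in six under the SAP boundary, or about one in eleven under the Protocol's p = 0.001. Such a trial would on average report about 23 to 27 points for a true 15 (about 29 under the Protocol's threshold, without overrun). Its 95% interval would miss the truth about 17–19% of the time instead of 5%, or about 31% under the Protocol's threshold. Under-coverage is worse for smaller true effects and disappears near 25 points, though the estimate is still too high there.

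The figures rest on a 50% placebo rate, 20% loss, a look at half the endpoints and, where stated, the assumed overrun. That the reported interval would be unadjusted is partly inferred from the SAP's silence together with Protocol section 9. The validity of the test is not in question. This is a change that should be made before any interim result is known, but it is not a flaw that undermines the design.

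**What to change.** - In SAP 4.1 and 6.2 and Protocol section 9, state that the primary risk difference is reported with a repeated confidence interval. It uses the spending-function critical value for the look at which the trial stops (2.96 at the interim or 1.97 at the end under the SAP schedule), updated to the actual schedule.
- State that it is computed on the final data set defined in SAP 3.6, including overrun.
- After an early stop, report a named bias-adjusted estimate (for example Whitehead's) beside the raw one. Restoring a general promise of adjusted intervals is not enough, because stage-wise ordering would satisfy it and change nothing at the first look.
- Reconcile the interim threshold in Protocol 3.5 (p = 0.001) with SAP 3.5 (Z = 2.96, about 0.003 two-sided), since the critical value depends on it.

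**Cost.** Wording only, with no change to sample size or data collection. After an early stop the interval is wider and conservative (about 97% coverage overall at the planned effect). It can still under-cover stopped trials when the true effect is 5 points or less. If the trial runs to the end, the result is almost unchanged.
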